#### 7.3.2 Subgroups

The primary endpoint will be analysed for the following participant subgroups:

1. Age (years): (a) <65 years and (b)  $\ge 65$ 

- 2. Sex at birth: (a) Male and (b) Female
- 3. Symptom duration (days): (a) <10 and (b)  $\ge 10$
- 4. Baseline 7-point ordinal scale: (a) 3, (b) 4 and (c) 5
- 5. Co-enrolment into RECOVERY: (a) Yes and (b) No
- 6. Co-treatment with dexamethasone: (a) Yes and (b) No (if a meaningful number if patients did not receive dexamethasone)

## 7.4 Missing Data

(ICH E3; 9.7.1, 11.4.2.2. ICH E9;5.3. EMA Guideline on Missing Data in Confirmatory Clinical Trials)

All reasonable efforts will be taken to minimise loss to follow-up, which is expected to be minimal as data collection for primary and secondary outcomes using trial-specific eCRFs is combined with linkage to routine clinical data on study outcomes. The number and percentage of participants with follow-up information at day 29 after the randomisation will be reported. For all participants who were discharged and alive but have missing clinical status, a clinical status scale of 2 (Not hospitalised, limitation on activities) will be applied.

## 7.5 Interim Analyses and Data Monitoring

(ICH E3; 9.7.1, 11.4.2.3. ICH E9; 4.1, FDA Feb 2010 "Guidance for Industry Adaptive Design Clinical Trials for Drugs and Biologics")

#### 7.5.1 Planned Schedule of Interim Analyses

No planned interim analysis but DMC has the rights to request for one.

#### 7.5.2 Scope of Adaptations

No planned interim analysis.

#### 7.5.3 Stopping Rules

For reasonable cause, the PI may terminate a participant's participation in the trial prematurely. The Sponsor may decide to terminate the trial prematurely. If this occurs, written notification of the trial termination is required to be sent to all the sites. Some conditions that may warrant trial termination include the following:

- Discovery of an unexpected, significant, or unacceptable risk to the participants in the trial,
- Decision on the part of the funder to suspend or discontinue development of the investigational product,
- Decision by a regulatory authority or the Sponsor to stop the trial at any time, were applicable.

If the trial is prematurely terminated, all participants who received a dose of any of the trial drugs and have not completed their trial period will be discontinued from the trial drug immediately; all the safety procedures required to be performed will be conducted. All discontinued participants will be followed up by a phone call 30 days after discontinuation for collection of AEs. The Sponsor will notify the appropriate Regulatory bodies in the respective countries regarding the reason for terminating the trial.

The DMC will evaluate the results of the trial in an unblinded fashion for safety. The DMC will also determine the adequacy of the assumptions in table 4 with regard to the proportion of patients experiencing the endpoints in the ordinary scale at day 29 on blinded data after at least 100 participants have been recruited. Following this interim evaluation the DMC may make the following recommendations to the TMG:

- 1 To continue the trial without modifications
- 2- To continue the trial with a modification of the sample size
- 3- To continue the trial with a change in the primary endpoint
- 4- To terminate the trial due to a low likelihood of achieving statistically significant results (futility)

## 7.5.4 Adjustment of Confidence Intervals and p-values

No planned interim analysis and adjustment of confidence intervals and p-values.

#### 7.5.5 Documentation of Interim Reports

Snapshots of the data available at each interim report to the DMC and/or TSC will be preserved. All documentation of analysis plans, programming code and reporting provided at each interim will be preserved.

## 7.6 Preliminary analysis

An analysis for preliminary efficacy and safety will be performed on an unlocked database using the full analysis population. The preliminary analysis will focus on the primary endpoints and a limited number of key secondary endpoints plus safety. The endpoints to be evaluated in the preliminary analysis are as follows:

Primary endpoint: Clinical Status on the WHO ordinal scale at day 29

Key secondary endpoints: Time to improvement on the ordinal scale, proportion of patients requiring mechanical ventilation, mortality, duration of hospitalization

Safety: Proportion of patients with one or more adverse events, proportion of patients with serious adverse events

Virologic efficacy of Brensocatib: Neutrophil elastase measurement in blood by treatment arm.

## 7.7 Multi-centre Studies

(ICH E3;9.7.1, 11.4.2.4. ICH E9; 3.2)

This is a multi-centre trial recruiting from 15 NHS Trusts/Boards within UK, if required to fulfil recruitment more NHS Trusts/Boards will be added.

Centre will be treated as random effect in the mixed ordinal logistic regression model and analysis of secondary outcomes.

## 7.8 Multiple Testing

(ICH E3; 9.7.1, 11.4.2.5. ICH E9; 2.2.5)

Due allowance for multiple testing will be made in the interpretation of the results: the larger the number of events on which a comparison is based and the more extreme the P-value after any allowance has been made for the nature of the particular comparison (i.e. primary or secondary; pre-specified or exploratory), the more reliable the comparison and, hence, the more definite any finding will be considered. 95% confidence intervals will be presented for the main comparisons.

## 8 Summary of Study Data

All continuous variables will be summarised using the following descriptive statistics: n (non-missing sample size), mean, standard deviation, median, maximum and minimum or median for non-normally distributed data with their interquartile range. The frequency and percentages (based on the non-missing sample size) of observed levels will be reported for all categorical measures. All summary tables will be structured with a column for each treatment in the order (Control, Experimental) and will be annotated with the total population size relevant to that table/treatment, including any missing observations.

## 8.1 Subject Disposition

The summary statistics will be produced in accordance with section 8.

#### 8.2 Protocol Deviations

Prospective, planned deviations or waivers to the protocol are not allowed under the UK regulations on Clinical Trials and must not be used, e.g. it is not acceptable to enrol a participant if they do not meet the eligibility criteria or restrictions specified in the trial protocol. The CI will not implement deviations to the protocol except where necessary to eliminate an immediate hazard to trial participants.

## 8.3 Demographic and Baseline Variables

Subject demographic data and baseline characteristics ((eg, sex, race/ethnicity, age and co-morbidities)) will be summarized by treatment group and overall using descriptive statistics (n, mean, SD, median, Q1, Q3, minimum, and maximum) for continuous data and by the number and percentage of participants for categorical data.

Age group (< 65 and  $\ge$  65) will be summarized by treatment group and overall.

#### 8.3.1 Other Baseline Characteristics

The following baseline disease characteristics will be summarized by treatment group and overall using descriptive statistics:

- Clinical status (7-point ordinal scale)
- Severity of illness
- Participants with confirmed SARS-CoV-2 PCR test and those treated as clinically suspected who never had a positive swab

## 8.4 Treatment Compliance

Trial drug compliance will be assessed by trial staff in hospitalised participants by checking drug returns and medication record sheet. The PI or delegate will collect unused medication and packaging from the clinical team. Where participants are discharged from hospital during the treatment phase, returns will not be requested, trial staff will ask participants at the day 29 phone call how many tablets are remaining and this will be recorded on the accountability log. Trial drug compliance will be assessed from the information provided by the participant and the above medication checks. For patients that attended for day 29 visits, medications will be returned and unused medication counted and documented.

## 8.5 Loss to follow-up

All reasonable efforts will be taken to minimise loss to follow-up, which is expected to be minimal as data collection for primary and secondary outcomes using trial-specific eCRFs is combined with linkage to routine clinical data on study outcomes. The number and percentage of participants with follow-up information at day 29 after the randomisation will be reported.

## 9 Efficacy Analyses

## 9.1 Primary Efficacy Analysis

The primary endpoint will be analysed using a mixed ordinal logistic regression, assuming proportional odds ratios adjusted for age and sites as a random effect. The odds ratio, 95% confidence interval and p-value for comparing treatments will be provided. The assumption of odds proportionality will be assessed using Brant Test of Parallel Regression Assumption. If the test indicate that proportional odds assumption is violated, the model will be run as a generalised ordered logistic model.

# 9.2 Secondary Efficacy Analyses

## 9.2.1 Time to clinical improvement (1 category)

The endpoint will be analysed with a time-to-event framework. Cox models will be used, and the survivor function will be estimated. The hazard ratio and 95% confidence interval will be provided. Participants without the endpoint being analysed will be censored on the day of the last non-missing ordinal scale assessment. The model will adjust for age and sites. Kaplan-Meier estimates for the time to event will also be plotted.

## 9.2.2 Clinical status at Day 3, 5, 8, 11, 15, 29

The number and percentage of participants in each clinical status category for day 3, 5, 8, 11, 15 and 29 will be summarized by treatment group. In addition, stacked bar charts by study day will be produced by treatment group using the definition specified in Section 4.3.

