3.7. Table of endpoints/outcomes

Objectives	Outcome Measures	Timepoint(s)
Primary Objective Participant clinical status (on a 7- point ordinal scale) In accordance with WHO recommendations the primary endpoint will be determined by a pilot trial of the first 100 participants.	 7-point ordinal scale: Not hospitalised, no limitations on activities Not hospitalised, limitation on activities; Hospitalised, not requiring supplemental oxygen; Hospitalised, requiring supplemental oxygen; Hospitalised, on non-invasive ventilation or high flow oxygen devices; Hospitalised, on invasive mechanical ventilation or ECMO (Extracorporeal membrane oxygenation) Death. 	Up to day 29
Secondary Objectives	Outcome Measures	Timepoint(s)
Evaluate the clinical efficacy of Brensocatib relative to standard care in adult patients hospitalised with COVID-19	Clinical Severity Time to an improvement of one category from admission using 7-point ordinal scale. Participant clinical status on 7-point ordinal scale Mean change in the 7-point ordinal scale	Daily whilst hospitalised Days 3, 5, 8, 11, 15 and 29. Baseline to days 3, 5, 8, 11, 15 and 29.
	National Early Warning Score (NEWS): Time to discharge or to a NEWS of ≤ 2 and maintained for 24 hours, whichever occurs first. Change from baseline Oxygenation:	Daily whilst hospitalised Days 8, 15, 29
	Oxygen free days Incidence and duration of new oxygen use during the trial	1-29 days 0-29 days
	Mechanical Ventilation: Ventilator free days	1-29 days

	Incidence and duration of new mechanical ventilation use during the trial.	1-29 days
	Hospitalisation:	
	Duration of hospitalisation (days).	Date of admission and discharge
	Mortality:	
	28-day mortality	Date of death
Evaluate the safety of the	Cumulative incidence of SAEs	1-29 days
intervention through 28 days of follow-up as compared to the control arm	Discontinuation or temporary suspension of treatment	1-29 days
	Changes in white cell count, haemoglobin, platelets, creatinine, total bilirubin, ALT, and AST over time (hospitalised participants only)	Days 0/1, 3, 5, 8, 11, 15, 29
	Adverse events of special interest- hyperkeratosis, infections and dental complications	1-29 days
	dental complications	
Exploratory Objectives	Outcome Measures	Timepoint(s)
Exploratory Objectives Evaluate the virologic efficacy of Brensocatib	·	Timepoint(s) Day 15 and day 29

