It is expected that these clinical assessments will be carried out by the clinical team during routine clinical care and documented on a NEWS chart. Where the assessments have been carried out, the results of the assessment closest to 8am on the day will be used to prevent duplication and further exposure of the trial staff to patients with COVID-19.

- Blood pressure and pulse, lying or seated
- Tympanic temperature
- SpO2
- Record if SpO2 has been measured on air or oxygen concentration the participant was receiving.

Ordinal Scale

The ordinal scale is an assessment of the clinical status on a given trial day. Each day, the worst score for that day will be recorded. The scale is as follows:

- 1. Not hospitalised, no limitations on activities
- 2. Not hospitalised, limitation on activities;
- 3. Hospitalised, not requiring supplemental oxygen;
- 4. Hospitalised, requiring supplemental oxygen;
- 5. Hospitalised, on non-invasive ventilation or high flow oxygen devices;
- 6. Hospitalised, on invasive mechanical ventilation or ECMO;
- 7. Death.

NEWS Score

The NEWS score has demonstrated an ability to discriminate patients at risk of poor outcomes. (Smith, 2016). This score is based on 7 clinical parameters. The NEWS2 Score is being used as an efficacy measure.

This should be evaluated at the assessment recorded closest to 8am on a given trial day. These parameters can be obtained from the hospital chart.

Exploratory assessment- viral shedding

Where practical at the Tayside site only, nasal swabs will be obtained on day 15 and day 29 to evaluate viral clearance by PCR.

Exploratory assessment- neutrophil studies

At the Tayside and Sheffield sites only, additional blood will be taken for isolation of peripheral blood neutrophils, as per outcome measures section 3.7.

Exploratory assessment- quality of life

The validated EQ-5D-5L quality of life tool will be administered to patients who are able to complete the questionnaire either in person (those still in hospital) or over the telephone (those at home) to determine the impact of treatment on quality of life.

Clinical Evaluation

As these participants are in-patients receiving care for COVID-19, they will be monitored as per clinical need. Where already obtained for clinical need the following blood results will be recorded at days 1, 3, 5, 8, 11, 15, 29:

- White cell count, haemoglobin, platelets, neutrophils, eosinophils, lymphocytes
- creatinine, eGFR
- AST and ALT

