#### National Early Warning Score (NEWS):

- 1. Time to discharge or to a NEWS of  $\leq$  2 and maintained for 24 hours, whichever occurs first.
- 2. Change from baseline to days 3, 5, 8, 11, 15 and 29

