#### 9.2.12 28-day mortality

All-cause mortality will be estimated using the Kaplan-Meier product limit method with all available data. The treatment arms will be compared using the log-rank test, and hazard ratios and 95% confidence intervals will be provided. Participants who did not die will be censored on the last study day.

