### NEWS Score, mean (SD)

Table 6: Primary outcome: Clinical status at day 29 according to treatment Group.

	Brensocatib	Placebo	Effect estimate (95%
	N =	N =	CI)
Clinical status at day 29 on the 7-point			
ordinal scale — no. of patients (%)			
Not hospitalised, no limitations on activities			
Not hospitalised, limitation on activities			
Hospitalised, not requiring supplemental oxygen			
Hospitalised, requiring supplemental oxygen			
Hospitalised, on non-invasive ventilation or high flow oxygen devices			
Hospitalised, on invasive mechanical ventilation or ECMO (Extracorporeal membrane oxygenation)			
Death			

Table 7: Secondary outcomes - Clinical Severity According to Treatment Group.

Brensocatib	Placebo	Effect estimate
N =	N =	(95% CI)

Time to clinical improvement (1 category)

Clinical status at Day 3 on the 7-point ordinal scale — no. of patients (%)

Not hospitalised, no limitations on activities

Not hospitalised, limitation on activities

Hospitalised, not requiring supplemental oxygen

Hospitalised, requiring supplemental oxygen

Hospitalised, on non-invasive ventilation or high flow oxygen devices

Hospitalised, on invasive mechanical ventilation or ECMO (Extracorporeal membrane oxygenation)

Death

Clinical status at Day 5 on the 7-point ordinal scale — no. of patients (%)

Not hospitalised, no limitations on activities

Not hospitalised, limitation on activities

Hospitalised, not requiring supplemental oxygen

Hospitalised, requiring supplemental oxygen

Hospitalised, on non-invasive ventilation or high flow oxygen devices

Hospitalised, on invasive mechanical ventilation or ECMO (Extracorporeal membrane oxygenation)

Death

Clinical status at Day 8 on the 7-point ordinal scale — no. of patients (%)

Not hospitalised, no limitations on activities

Not hospitalised, limitation on activities

Hospitalised, not requiring supplemental oxygen

Hospitalised, requiring supplemental oxygen

Hospitalised, on non-invasive ventilation or high flow oxygen devices

Hospitalised, on invasive mechanical ventilation or ECMO (Extracorporeal membrane oxygenation)

Death

Clinical status at Day 11 on the 7-point ordinal scale — no. of patients (%)

Not hospitalised, no limitations on activities

Not hospitalised, limitation on activities

Hospitalised, not requiring supplemental oxygen

Hospitalised, requiring supplemental oxygen

Hospitalised, on non-invasive ventilation or high flow oxygen devices

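### SAP 9.2.1 and 9.2.4 set no rule for deaths in two time-to-recovery analyses; as most naturally read, deaths are censored at death, Kaplan-Meier overstates improvement and a survival benefit is ignored or can lower the hazard ratio

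*SAP*

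**What the plan says.** SAP 9.2.1 (time to a one-category improvement) and SAP 9.2.4 (time to discharge or NEWS of 2 or less) contain the same sentence: "Participants without the endpoint being analysed will be censored on the day of the last non-missing ordinal scale assessment". Both then call for a Cox model with a hazard ratio and 95% confidence interval, and both add that "Kaplan-Meier estimates for the time to event will also be plotted". Neither section mentions death, and the SAP names no competing-risk method.

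The NEWS endpoint in SAP 4.2 is discharge or the NEWS threshold, "whichever occurs first"; death is not part of the event. On the ordinal scale death is category 7, and Protocol 7.8 says "Each day, the worst score for that day will be recorded". Protocol 3.7 has time to improvement assessed "Daily whilst hospitalised".

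Three other places bear on how deaths are handled:

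- SAP 16 includes "Table 6: Primary outcome: Clinical status at day 29 according to treatment Group", and that table has a row for death.
- SAP 7.4 has one fill-in rule for clinical status. It covers only participants who left hospital alive and whose status is missing.
- SAP 9.2.12 analyses mortality separately and there gives an explicit rule: "Participants who did not die will be censored on the last study day".

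SAP 7.6 lists time to improvement among the "Key secondary endpoints: Time to improvement on the ordinal scale" group for the preliminary analysis.

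**The concern.** Both endpoints are times to a good outcome that death rules out for good. Ordinary censoring assumes that a person who leaves follow-up would go on to have the event at the same rate as those who remain. That is tenable for a living participant lost to follow-up. It is false for one who has died.

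Two things are at stake. The first is the Kaplan-Meier curve. If deaths are censored at death, the curve shows a larger share of participants improving than actually improve, whatever the drug does. The second is the meaning of the hazard ratio. It would compare recovery rates among those still alive and event-free, so a drug that prevents deaths gets no credit for that, and its hazard ratio can fall if the people it saves recover slowly. Because the rule for deaths is unstated, two programmers could also produce different hazard ratios from one dataset.

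**Working it through.** **1. Which reading the text supports.** Under reading A, the last assessment of someone who dies is at about the day of death, so that person is censored there. Under reading B, category 7 is carried to day 29, so that person stays in the risk set as not improved. Reading A is more natural: the scale is scored for a given trial day, it is collected daily in hospital, and the only fill-in rule (SAP 7.4) covers living participants. Reading B is possible because a participant who died earlier must count as category 7 in the day-29 primary table.

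**2. The plan's own figures.** The documents give no figure for these two endpoints. The only mortality they assume is 2% in the placebo arm (Protocol Table 4, SAP Table 2). That distribution reproduces the stated sample size. With N = 12(z_a + z_b)² / [ln(OR)² (1 − Σp̄³)], z_a + z_b = 1.960 + 1.036, OR = 2 and Σp̄³ = 0.1686:

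N = 12 × 8.978 / (0.4805 × 0.8314) = 269.7, against 272 stated.

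Nothing in that calculation involves the censoring rule.

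**3. Kaplan-Meier overstatement, simplest case.** Assume a constant daily recovery hazard r = 0.12 and a constant death hazard d chosen to give the stated mortality by day 29. Censoring at death gives 1 − exp(−29r). The true proportion improving is [r/(r+d)] × [1 − exp(−29(r+d))].

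- 2% mortality, d = 0.00252: 1 − exp(−3.48) = 96.9%; truth 0.9794 × 0.9714 = 95.1%; gap 1.8 points.
- 10% mortality (assumed), d = 0.01365: 96.9%; truth 0.8979 × 0.9793 = 87.9%; gap 9.0 points.

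**4. Both readings compared.** This is an expected-count calculation in daily steps over 29 days with 1:1 allocation. The drug halves the death hazard and has no effect on recovery. In the slow-recoverer case, 20–30% of participants have a recovery hazard of 0.01–0.03 and carry all the deaths; the rest have 0.15. Mortality above 2%, the hazards and the halving are assumptions.

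| Placebo mortality | Uniform prognosis: HR, deaths censored / kept to day 29 | Deaths in slow recoverers: HR, censored / kept | Slow recoverers: placebo Kaplan-Meier excess (points) |
|---|---|---|---|
| 2% | 1.00 / 1.02 | 0.994–0.996 / 1.002–1.007 | 0.9–1.2 |
| 5% | 1.00 / 1.05 | 0.985–0.989 / 1.006–1.016 | 2.3–3.2 |
| 10% | 1.00 / 1.10 | 0.965–0.976 / 1.011–1.032 | 5.2–7.3 |
| 15% | 1.00 / 1.14 | 0.935–0.959 / 1.016–1.043 | 8.7–13.2 |

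**5. A second model, varying who is saved.** Here recovery times are exponential with mean 9 days, death times are gamma(3, 4) capped at day 29, and the drug has no effect on recovery itself.

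- 2% v 1%, those saved stay ill to day 29: HR 0.98 with deaths censored, 1.00 with deaths kept. Control Kaplan-Meier is 95.7% against a true 94.1%, a gap of 1.6 points.
- 10% v 6%, those saved stay ill: 0.94–0.96 censored, 1.00–1.02 kept. Control Kaplan-Meier is 93–94% against a true 86%, a gap of 7–8 points.
- 10% v 6%, death independent of recovery: about 1.00 censored.
- 10% v 6%, those saved recover like other survivors: 1.06 censored.
- Harm, 10% rising to 15%, extra deaths among people who would have recovered normally: 0.93 censored, 0.89 kept.
- Harm, 10% rising to 15%, extra deaths among people who would have stayed ill: 1.07–1.08 censored, 0.99–1.00 kept.

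The Kaplan-Meier excess appears in every case. The shift in the hazard ratio changes sign with the prognosis of those who die.

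**The case against.** A reader might infer that the SAP censors deaths at death as a stated rule. It does not say so. Carrying category 7 to day 29 is compatible with the text and would already keep deaths in the risk set. That stands, and it makes the defect an unstated rule whose natural reading is the problematic one.

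A reader might also infer that a survival benefit counts against the drug. The documents do not support that as a general statement. It needs the people saved to be slow recoverers. Protocol section 1 makes this plausible, since it links most deaths to ARDS after slow deterioration, but nothing in the documents establishes it. With uniform prognosis the benefit is ignored, and if those saved recover normally the hazard ratio rises.

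The cause-specific hazard ratio is a recognised quantity. Keeping deaths to day 29 mixes mortality into recovery: with no effect on recovery and uniform prognosis, it gives 1.10 at 10% mortality. This is a fair reason to report both, but it does not rescue the Kaplan-Meier curve.

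At the plan's 2% mortality the shift is small beside sampling error. With 400 participants and about 94% having the event, the standard error of the log hazard ratio is about 2/√376 = 0.10. Deaths also count as the worst category of the primary endpoint, in SAP 9.2.12 and in the safety listings. Time to improvement is called key only for the preliminary analysis; SAP 4.2 lists it as an ordinary secondary endpoint. All of this limits the importance of the point. None of it supplies the missing rule.

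**Conclusion.** The point holds as a gap that should be closed for two secondary endpoints. The SAP does not say how deaths are handled, and its natural reading censors them at about the day of death. The two possible readings give different hazard ratios from the same data.

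Under censoring at death, one minus Kaplan-Meier overstates improvement by about 1.6 points at the plan's 2% mortality (0.9 to 1.8 across the models shown). At an assumed 10%, with deaths in people who would not soon recover, the excess is about 5 to 8 points. This needs no treatment effect.

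The hazard ratio is then cause-specific. A survival benefit is ignored, or lowers it if those saved recover slowly: by about 0.02 or less at 2% mortality and by up to about 0.06 at an assumed 10% v 6%. The direction cannot be settled from the documents, because it depends on who dies. Mortality above 2% is an assumption; the plan itself calls its outcome distribution uncertain. The primary endpoint and the sample size are unaffected.

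**What to change.** In SAP 9.2.1 and 9.2.4:

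1. State that participants who die before the event stay in the risk set as not improved, or not discharged, and are censored at day 29.
2. Replace the Kaplan-Meier plot with cumulative incidence curves that treat death as a competing event.
3. Keep censoring at the last assessment for living participants lost to follow-up.
4. Report the cause-specific hazard ratio, with deaths censored at death, as a supporting result.

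The cost is a couple of sentences in the SAP, one recoded time variable and a different plot. The downside is that the main hazard ratio becomes a subdistribution-type ratio that mixes mortality with recovery. It needs a footnote saying so and should be read beside the cause-specific result and the mortality analysis. The wording should be fixed before any results by treatment arm are seen, including those of the preliminary analysis.

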#### Secondary outcome

## Clinical severity:

- 1. Time to an improvement of one category from admission to day 29 using 7-point ordinal scale
- 2. Clinical status on 7-point ordinal at days 3, 5, 8, 11, 15 and 29
- 3. Change on 7-point ordinal from baseline to day 15
- 4. Proportion of participants showing improvement on 7-point ordinal scale at day 15
- 5. Mean change in the 7-point ordinal scale from baseline (day 1) to days 3, 5, 8, 11, 15 and 29.

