## 4.3 Derived variables

The primary endpoint is an assessment of the clinical status on a given trial day using a 7-point ordinal scale. Each day, the worse score for will be recorded. The scale is as follows:

- 1. Not hospitalised, no limitations on activities
- 2. Not hospitalised, limitation on activities;
- 3. Hospitalised, not requiring supplemental oxygen;
- 4. Hospitalised, requiring supplemental oxygen;
- 5. Hospitalised, on non-invasive ventilation or high flow oxygen devices;
- 6. Hospitalised, on invasive mechanical ventilation or ECMO;
- 7. Death.

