## 9.2.6 No of days free from oxygen

Number of days free from oxygen support will be compared between the treatment arms using the negative binomial regression with time in ICU as the offset. Number of days will be calculated as the number of days free from oxygen support reported on the 7-point ordinal scale eCRF.

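### SAP 9.2.1 leaves entry category out of the Cox model for time to a one-category improvement, which costs sensitivity if improvement rates differ between categories

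*SAP*

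**What the plan says.** SAP 4.2, under clinical severity, defines the endpoint as "Time to an improvement of one category from admission to day 29 using 7-point ordinal scale". SAP 9.2.1 gives the analysis: "Cox models will be used, and the survivor function will be estimated", with a hazard ratio and 95% confidence interval, and then "The model will adjust for age and sites. Kaplan-Meier estimates for the time to event will also be plotted". No other covariate and no stratum is named.

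The SAP expects patients to enter in three categories. The subgroup list in 7.3.2 reads "Baseline 7-point ordinal scale: (a) 3, (b) 4 and (c) 5". On the scale in SAP 4.3, category 3 is "Hospitalised, not requiring supplemental oxygen", category 4 is "Hospitalised, requiring supplemental oxygen", and category 5 is hospital care on non-invasive ventilation or high-flow oxygen. Randomisation is stratified by site and age only (SAP 5.3).

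SAP 7.3.1 allows the baseline ordinal score to be added should that be thought needed. The sentence sits in the paragraph on the primary analysis, gives no decision rule, and is not repeated in 9.2.1. SAP 7.6 lists the endpoint first among those for the preliminary analysis: "Key secondary endpoints: Time to improvement on the ordinal scale".

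**The concern.** One step on the scale means leaving hospital for a patient in category 3, a day without oxygen for a patient in category 4, and a day off non-invasive ventilation or high flow for a patient in category 5. A single Cox model gives all three a common baseline hazard apart from age and site. If the three steps happen at different speeds, entry category is a prognostic factor left out of the model.

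Leaving such a factor out of a Cox model has a known effect even when the drug works equally well in every category. The fast category empties sooner in the better arm, so the patients still at risk in that arm come increasingly from the slow categories. The pooled hazard ratio then drifts towards 1 over follow-up, and the test loses power. The pooled Kaplan-Meier curve becomes a mixture of three processes. What is at stake is the sensitivity and readability of one secondary endpoint.

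**Working it through.** **The plan's own figures.** The documents state no hazard ratio, event count or power for this endpoint. The sample size concerns the primary ordinal outcome, and it reproduces. Whitehead's formula is N = 12(z₁ + z₂)² / [(ln OR)²(1 − Σp̄³)]. With 1.960 and 1.036 for two-sided 5% and 85% power, OR 2, and Σp̄³ = 0.169 from the mean of the two columns of SAP Table 4, N = 12 × 8.98 / (0.480 × 0.831) = 270, against 272 stated. This settles nothing about the Cox model, but it confirms the basis of the trial size used below.

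**Mechanism, one worked case.** Assume a mix of 30/50/20% in categories 3/4/5, placebo medians of 3/7/14 days, exponential times, and a true hazard ratio of 1.30 in every category. The pooled hazard at time t is Σpλ S(t) / Σp S(t), where λ = ln 2 / median.
- At day 0 the ratio between arms is exactly 1.30.
- At day 14 the placebo survivor fractions are 0.039, 0.250 and 0.500, so the pooled hazard is 0.02006 / 0.2368 = 0.0847.
- At day 14 the treated fractions are those values to the power 1.30: 0.015, 0.165 and 0.406. The pooled hazard is 0.01719 / 0.1682 = 0.1022.
- The ratio at day 14 is 0.1022 / 0.0847 = 1.21.

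The pooled ratio has fallen from 1.30 to 1.21 although the effect within each category never changed.

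**Size by simulation.** Inputs from the documents: 400 patients, 1:1, two-sided 5%, follow-up to about day 29, entry categories 3/4/5. Assumptions: category mix, medians, hazard ratio. Power is the share of simulated trials with a significant result. Each cell shows power without strata v with strata by entry category, true hazard ratio 1.35, 1,500 runs:

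| Medians (days) | Mix 10/80/10 | Mix 20/65/15 | Equal thirds |
|---|---|---|---|
| 5/6/8 | 84.2 v 84.1 | 80.4 v 80.6 | 81.4 v 84.1 |
| 4/6/10 | 79.7 v 81.9 | 76.3 v 80.9 | 75.8 v 82.7 |
| 3/6/14 | 75.0 v 81.3 | 70.1 v 82.3 | 61.6 v 79.7 |

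The losses by row are about 0 to 3, 2 to 7, and 6 to 18 points. With equal medians (6/6/6) there is no loss (83.0 v 82.6 with equal thirds). In the 3/6/14 row the pooled hazard ratio averages 1.31, 1.29 and 1.26, and the stratified one about 1.35 throughout. With a mix of 20/65/15 and category 3 slowest (8/5/5), power is 80.1 v 83.1, so the loss does not require that category 3 improves fastest.

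A second set used a true hazard ratio of 1.30, mix 30/50/20, times in whole days and Efron ties:
- 5/6/8: hazard ratio 1.29 v 1.30, power 71% v 72%
- 4/6/12: 1.27 v 1.31, 63% v 73%
- 3/7/14: 1.25 v 1.30, 57% v 71%

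Repeat runs of the 3/7/14 case gave losses between 12 and 19 points, which shows the simulation error. With a true hazard ratio of 1.0, rejection was 4 to 6% with and without strata.

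**What was not simulated.** Age and site effects and deaths were left out. Age adjustment may recover a little of the loss.

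**The case against.** The strongest reply is that this is an efficiency choice. Adjusting for the randomisation factors is coherent, the test keeps its size, and the unstratified hazard ratio is a legitimate marginal quantity, so part of the move towards 1 is a change in what is estimated. That stands. A reader might infer from the pooling of three events that the planned result is invalid or prone to false positives. Neither the documents nor the simulations support that.

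Nor do the documents show that improvement rates differ by entry category, or in which order. That also stands: with equal rates nothing is lost, and losses above 10 points need a wide spread. It would be wrong to say flatly that the planned analysis loses power.

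The weight of the endpoint can also be disputed. SAP 7.6 calls it key only for the preliminary analysis, 9.2.1 promises an estimate and interval without a p-value, and there is no power target for it. Power here is therefore best read as a measure of precision.

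The optional wording in SAP 7.3.1 shows that the authors had the covariate in mind. It does not answer the point. It belongs to the primary analysis, and if stretched to cover 9.2.1 it would leave the model open while SAP 7.6 plans a comparison of this endpoint on an unlocked database.

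A reader might extend the argument to the oxygen-free and ventilation-free day models in SAP 9.2.6 and 9.2.9, which also name no baseline covariate. No size can be given there, because the planned negative binomial model with an ICU-time offset was not tested.

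**Conclusion.** The point holds as a conditional loss of sensitivity. SAP 9.2.1 omits the one variable that determines what the event is, and no other section of the SAP puts it back. If improvement rates are similar across categories 3, 4 and 5, the omission costs nothing. If they differ, the hazard ratio is drawn towards 1. The cost in power is about 0 to 3 points for a mild spread (5/6/8), 2 to 7 for a moderate one (4/6/10) and roughly 6 to 18 for a strong one (3/6/14 or 3/7/14). These figures rest on assumed mixes, medians and a constant hazard ratio of 1.30 to 1.35 within category, because the documents supply none of these.

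The case for changing the plan rests on asymmetry: stratifying costs essentially nothing when rates are equal and recovers the loss when they are not.

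**What to change.** In SAP 9.2.1, stratify the Cox model by baseline ordinal category (3, 4, 5), with a stated rule for merging any other or sparse category. The rule is needed because the table shell for status at randomisation lists all seven. Keep age and sites as planned. Show Kaplan-Meier curves by arm within category as well as overall.

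Settle the reference point in the same edit. SAP 4.2 counts improvement from admission, but randomisation may come up to 96 hours later (SAP 5.2.1), and the mean-change endpoint in the same list uses baseline, day 1. If the event is counted from one status and the strata use another, each stratum can still mix different events. The day 1 score also needs care. The worst score of each day is recorded (SAP 4.3), and day 1 is the day of the first dose (SAP 5.4), so that score may reflect hours after dosing. State one status, recorded before the first dose, and use it both to define the event and to form the strata. Clinical status is already scheduled at screening and at randomisation.

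The cost is a few lines of SAP text and one model option. The hazard ratio becomes conditional on entry category, which the report should say, and there is slightly more output. The change should be fixed before anyone choosing the model sees this endpoint by arm, including in the preliminary analysis.
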